6.11 Clinical Follow-up (All registered subjects)

Follow-up visits are required at 1 week (phone contact), 30 days, 6 months, 12 months, 18 months, 24 months, and annually thereafter through 5 years. For all randomized subjects, follow-up visits will be calculated from the date of the “Treatment” visit and for roll-in subjects, follow-up visits will be calculated from the date of the index procedure. Follow-up assessments can be performed at any point in the window, and should be conducted, whenever possible, by the same individual who performed the baseline tests. The subject should be followed at the investigational site where the subject was registered, and may be followed at another investigational site only with prior agreement from that site’s Investigator and from the Sponsor.

Subjects should have their blood pressure checked at each scheduled in-clinic visit. Subjects should be prescribed medication as necessary following current standard of care to maintain normotensive blood pressure.

All subjects, regardless of randomization assignment or roll-in designation, should continue to be monitored and treated per applicable standards of care consistent with the subject’s condition. All subjects must be followed by the heart failure specialist investigator at all scheduled follow-up visits. Subjects implanted with the MitraClip device must also be evaluated for device integrity. The site Principal Investigator should collaborate with the other site investigators as applicable in determining the treatment strategy for all subjects registered at their site. The electronic case report forms will document changes in treatment strategy (i.e. new use of CRT, PCI, and mitral valve surgery) and who was involved with determining changes in treatment strategy.

Study personnel administering the 6MWT and QoL questionnaires from baseline through 24 months excluding the 18-month visit and assessing NYHA Functional Class from baseline through the 5 year visit will be blinded, i.e., will not have access to the eCRF and will not have knowledge of the subject's treatment assignment. Additionally, a standardized script will be used when administering the assessments and the subject will be reminded to not reveal their treatment history to the administrator (See **Section 10.14 Measures Taken to Avoid and Minimize Bias During Study Conduct** for additional information).

To support the primary effectiveness endpoint analysis, clinical sites and all randomized subjects (or their identified contacts) will be contacted to determine each subject's survival status and date(s) of last known heart failure hospitalizations. This data sweep of death and heart failure hospitalizations will be conducted when the last randomized subject has passed the upper limit of the window for the 12-month follow-up period (i.e., 395 days after enrollment). The sweep contact is not needed for subjects who had a follow-up visit within 30 days of the sweep date, or for subjects who already completed their 24-month follow-up visit.

6.11.1 1-Week Phone Contact

All subjects will be contacted by telephone at the 1-week visit. Sites will follow a standardized script for all subjects to minimize bias. Additionally, for Device group or roll-in subjects who underwent the MitraClip procedure, the script will include a query about adverse events, including suspected skin injury.

6.11.2 30-Day, 6-Month, 12-Month, 18-Month and 24-Month Visits

During the physical examination at the 30-day follow-up clinic visit, the implanting or treating investigator shall examine the integrity of the Device group or roll-in subject's skin at or near the beam entrance site for subjects that have undergone a MitraClip procedure. At the 30-day, 6-month, 12-month, 18-month and 24-month follow-up visits, all subjects must be examined by the heart failure specialist investigator. Subjects must continue to take baseline medications without change during follow-up, unless clinically (medically) necessary. If there are any cardiovascular medication changes (including dosage changes), these changes, and the reason for change must be documented on the electronic case report form. In general, neurohormonal antagonists should not be changed. Subjects implanted with the MitraClip device must also be evaluated for device integrity. Required tests and procedures outlined below must be completed. All visits and tests must be completed even if the subject is in hospital.

- 12-lead ECG
- Blood draw

- Brief physical exam including vital signs (weight, heart rate, blood pressure and temperature)
- Echocardiogram (TTE)
- Modified Rankin Scale (Assessment of mRS should additionally be done at 90 days after onset of stroke) (not required after 12 months)
- 6-Minute Walk Test (6MWT) (not required at 18 months) – See **APPENDIX E: ATS 6 Minute Walk Test Guidelines** – must be administered by “blinded” study personnel
- Concomitant cardiovascular medications assessment
- NYHA Functional Class assessment – must be administered by “blinded” study personnel
- QoL questionnaires to be completed by the subject (not required at 18 months) – must be administered by “blinded” study personnel; Note: To minimize bias and undue influence, the QoL questionnaires will be completed by the subject, unless the subject is unable to complete the questionnaire on their own (in such cases, a note to file must be completed to document the inability of subject to complete the questionnaire)
- Assess and record adverse events
- Assess and record protocol deviations

Instructions for the TTE are provided in **APPENDIX B: Echocardiography Protocol**.

6.11.3 3, 4 and 5 Year Visits

Medications should be recorded and required tests and procedures outlined below should be completed. All subjects must be examined by the heart failure specialist investigator. Subjects must continue to take baseline medications without change during follow-up, unless clinically (medically) necessary. If there are any cardiovascular medication changes (including dosage changes), these changes, and the reason for change must be documented on the electronic case report form. In general, neurohormonal antagonists should not be changed. Subjects implanted with the MitraClip device must also be evaluated for device integrity. Required tests and procedures outlined below must be completed. All visits and tests must be completed even if the subject is in hospital.

- 12-lead ECG
- Brief physical exam including vital signs (weight, heart rate, blood pressure and temperature)

- Concomitant cardiovascular medications assessment
- Echocardiogram (TTE)
- NYHA Functional Class assessment
- Assess and record adverse events
- Assess and record protocol deviations

Instructions for the TTE are provided in **APPENDIX B: Echocardiography Protocol**.

[figure not shown]

Figure 3: Trial Flowchart

After the “Treatment” visit, the investigational sites will be provided the target date and required follow-up window time-frames for each subject in the electronic data capture system. Follow-up windows are summarized in **Table 1: Follow-up Schedule* and Windows for Registered Subjects**. All data required for follow-up must be collected within the window for that scheduled visit, and not necessarily on the same day.

Table 1: Follow-up Schedule* and Windows for Registered Subjects

| Follow-Up Visit | Window Start Day | Target Day | Window Close Day | Follow up Method |
|----------------------------------|------------------|----------------|------------------|---------------------------|
| Discharge (Device group only) | NA | Discharge date | NA | In hospital or Site visit |
| 1 Week (-1 /+3 days) | 6 | 7 | 10 | Phone contact |
| 30 Days (-3 /+14 days) | 27 | 30 | 44 | Site visit |
| 6 Months (±30 days) | 152 | 182 | 212 | Site visit |
| 12 Months (-14/+30 days) | 351 | 365 | 395 | Site visit |
| 18 Months (±30 days) | 518 | 548 | 578 | Site visit |
| 24 Months (±30 days) | 701 | 731 | 761 | Site visit |
| 3 Years (±45 days) | 1051 | 1096 | 1141 | Site visit |
| 4 Years (±45 days) | 1416 | 1461 | 1506 | Site visit |
| 5 Years (±45 days) | 1781 | 1826 | 1871 | Site visit |

* Follow-up visit dates are calculated from the “Treatment visit” for randomized subjects and from the index procedure for roll-in subjects

Echocardiography images (TTE) obtained at each follow-up visit should be submitted to the Sponsor in a timely manner. The ECL will provide feedback to sites regarding quality of images obtained.

During the follow-up period, if a subject requires a cardiac procedure (i.e. MV surgery, permanent LVAD, heart transplant, additional MitraClip procedure, etc.) which may or may not result in explant of the MitraClip device, the subject will remain in the trial and continue to be followed.

Subjects who do not have a scheduled follow-up visit will be documented as having a missed visit and a Protocol Deviation will be completed. The investigator will keep a record of

documented follow-up attempts in the subject's study file. Refer to Section **10.10 Protocol Deviations** for additional information.

Table 2 provides a complete listing of required tests and procedures for all subjects through the trial follow-up period.

Table 2: Clinical Evaluation Schedule for Registered Subjects

| Items | Screening/ Baseline | Randomization Assignment (For randomized Subjects only) | Treatment Visit (Control Group) | Treatment Visit (Device Group or Roll-in) | Discharge (Device Group or Roll-in) | 1-Week Phone Contact | 30-Days ^d , 6, 12, 18, 24 Months | 3, 4, 5 Years |
|--|---|--|---------------------------------------|--|--|----------------------------|---|------------------|
| Informed Consent | X | | | | | | | |
| Medical History | X within 90 days pre-registration | | | | | | | |
| Evaluation by Local Heart Team including HF Specialist Investigator and CT Surgeon Investigator (in-person consult with HF specialist and CT Surgeon investigators is required). | X within 90 days pre-registration | | X | | | | X | X |
| Components of Frailty Index | X within 14 days pre-registration | | | | | | | |
| STS Risk Score | X within 90 days pre-registration | | | | | | | |
| Modified Rankin Scale ^a | X within 14 days pre-registration | | | | X | | X not required after 12-month visit | |
| Physical Examination & Vital Signs: (height (at Baseline only), weight, heart rate, blood pressure and temperature) | X within 14 days pre-registration | | X | X within 24 hours pre- procedure | X | | X | X |
| Concomitant Cardiovascular Medications | X | | X | X | X | | X | X |
| 12-lead ECG | X within 90 days and 14 days pre- registration | | | X within 24 hours pre- procedure | X | | X | X |
| Transthoracic Echocardiogram ^b | X within 90 days pre-registration | | | | X | | X | X |

| Items | Screening/ Baseline | Randomization Assignment (For randomized Subjects only) | Treatment Visit (Control Group) | Treatment Visit (Device Group or Roll-in) | Discharge (Device Group or Roll-in) | 1-Week Phone Contact | 30-Days ^d , 6, 12, 18, 24 Months | 3, 4, 5 Years |
|---|--|--|---------------------------------------|--|--|----------------------------|---|--------------------------------------|
| Transesophageal Echocardiogram | X within 180 days pre-registration | | | X within 3 days pre- procedure | | | | |
| Albumin | X within 14 days pre-registration | | | | | | | |
| CBC with differentials and platelet count Serum Creatinine PTT or PT or INR CK, CK-MB | X within 14 days pre-registration | | | | X | | X | |
| BNP or NT-proBNP ^c | X within 90 days pre-registration | | | | | | X | |
| 6 Minute Walk Test Quality of Life Questionnaires (KCCQ and SF-36) | X within 14 days pre-registration (by blinded study personnel) | | | | | | X (by blinded study personnel) not required at 18-month visit | |
| NYHA Functional Class | X within 90 days and 14 days pre- registration (by blinded study personnel) | | | | | | X (by blinded study personnel) | X (by blinded study personnel) |
| Inquiry of Subject Status | | | | | | X | | |
| Adverse Events | | X ^c | X | X | X | X | X | X |

^a Assessment of mRS should also be done 90 days after onset of stroke

^b TTE for the purpose of determining eligibility must be obtained after the subject has been stabilized on optimal therapy including GDMT and undergone revascularization and/or CRT, as appropriate (see **APPENDIX A: Definitions** for definition of optimal therapy and GDMT), and submitted to the ECL. A TTE must also be performed within 90 days prior to any additional MitraClip procedure or mitral valve surgery.

^c BNP or NT-proBNP must be measured after the subject has been stabilized on GDMT and undergone revascularization and/or CRT, as appropriate (see **APPENDIX A: Definitions** for definition of GDMT)

^d A 30-day visit should be performed 30 days after mitral valve surgery or MitraClip procedure in the Control group and after mitral valve surgery or additional MitraClip procedure in Device group or roll-in subjects per the requirements specified in **Section 6.13.1 30-Day Post-MitraClip Follow-up** and **Section 6.14.1 30-Day Post-Mitral Valve Surgery Follow-up**.

^e Adverse events must be collected upon trial registration for roll-in and randomized subjects

NOTE: When the last randomized subject has passed the upper limit of the window for the 12-month follow-up, subjects (or their identified contacts) will be contacted to determine survival status and date(s) of last known heart failure hospitalizations. See **Section 6.11 Clinical Follow-up (All registered subjects)** for details.

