7.4.7 Recurrent Hospitalization - All-Cause

Treatment with the MitraClip device may reduce the risk of recurrent all-cause hospitalization.

Hypothesis:

The null and alternative hypotheses are stated as:

$$\mathbf{H_0: } RRR \leq 0 \text{ vs.}$$

$$\mathbf{H_1: } RRR > 0$$

where RRR is the relative risk reduction in the rate of recurrent hospitalization due to treatment with the MitraClip device. All hospitalizations will be included as events in the analysis.

¹⁸ D. M. Finkelstein and D. A. Schoenfeld, Combining Mortality and Longitudinal Measures in Clinical Trials, *Statistics in Medicine* 1999;18:1341-54..

Analysis:

This endpoint will be analyzed when the last subject completes 12 months of follow-up. All available follow-up through 24 months at the time of data cut-off will be included in the analysis. Subjects who do not experience any hospitalizations will be censored on their data cut-off date. Subjects who die will be censored on the date of death. Subjects who withdraw from the trial will be censored on the date of withdrawal.

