## **Hypothesis:**

The null and alternative hypotheses are stated as:

 $H_0$ : RRR = 0 vs.

 $\mathbf{H_1}$ : RRR  $\neq 0$ 

where RRR is the relative risk reduction in the rate of recurrent hospitalization due to treatment with the MitraClip device. All hospitalizations will be included as events in the analysis.

The Joint Frailty Model method will be used to model the recurrent hospitalization data and estimate the RRR.

RRR = (1- Hazard Ratio of Device vs. Control) =  $(1 - e^{\beta})$  where  $\beta$  is the regression coefficient of the recurrent hospitalization in the JFM model.

This endpoint will be analyzed when the last subject completes 12 months of follow-up. All available follow-up through 24 months at the time of data cut-off will be included in the analysis. Subjects who do not experience any hospitalizations will be censored on their data cut-off date. Subjects who die will be censored on the date of death. Subjects who withdraw from the trial without a hospitalization will be censored on the date of withdrawal.

The null hypothesis is rejected if the regression coefficient for the Device group is significant at the two-sided significance level of 5%. The two-sided 95% confidence interval is calculated as RRR  $\pm$   $Z_{\alpha/2} \times$  SE where RRR and SE are estimated from the Joint Frailty Model and  $Z_{\alpha/2} = 100(1-\alpha/2)$ th percentile of the standard normal distribution. Beneficial treatment effect is established if the lower two-sided 95% confidence bound of the relative risk reduction is greater than zero.

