#### 5.9 Multiplicity Adjustments

Both the primary safety and primary effectiveness endpoints must be met for trial success.

The secondary endpoints will be evaluated for labeling claims if both primary endpoints are met. The secondary endpoints will be tested sequentially in the following order:

- MR Severity of  $\leq 2+$  at 12 months
- All-Cause Mortality at 12 months (Non-inferiority test)
- Hierarchy of death and recurrent HF hospitalization (analyzed when the last subject completes 12 months of follow-up)
- Change in KCCQ score at 12 months from baseline
- Change in 6MWD at 12 months from baseline
- Recurrent hospitalizations all-cause (analyzed when the last subject completes 12 months of follow-up)
- NYHA Functional Class of I/II at 12 months
- Change in Left Ventricular End Diastolic Volume at 12 months
- All-Cause Mortality (Superiority test, if HR < 1) (analyzed when the last subject completes 12 months of follow-up and use all available data up to 24 months)
- Composite 30-Day Secondary Safety Endpoint

The multiplicity adjustments above are only performed for the primary analyses (ITT) of the primary and secondary endpoints.

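### The pre-analysis sweep asks only about survival and heart failure admissions, so the confirmatory all-cause hospitalization endpoint relies on passive reporting for other admissions since the last visit

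*Protocol*

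**What the plan says.** Protocol Section 6.11 ties the sweep to one endpoint: "To support the primary effectiveness endpoint analysis, clinical sites and all randomized subjects (or their identified contacts) will be contacted". What is sought is each subject's "survival status and date(s) of last known heart failure hospitalizations". Some subjects are exempt: "The sweep contact is not needed for subjects who had a follow-up visit within 30 days of the sweep date", and so are those who have completed the 24-month visit. The note under Table 2 repeats the restricted content: subjects or their contacts "will be contacted to determine survival status and date(s) of last known heart failure hospitalizations".

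The all-cause endpoint is wider. Protocol Section 7.4.7 states: "All hospitalizations will be included as events in the analysis". SAP Section 5.6.2.7 says of its data window: "All available follow-up through 24 months at the time of data cut-off will be included in the analysis". On censoring it says: "Subjects who do not experience any hospitalizations will be censored on their data cut-off date". SAP Section 5.9 puts this endpoint sixth in the ordered list tested for labeling claims. No section of either document extends the sweep to admissions other than heart failure.

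There is another route for these admissions. In-patient hospitalization is a serious adverse event (SAE) criterion (Protocol 8.1.2). Adverse events are taken from subject report, investigator observation or medical records (8.4.1). SAEs are due to the sponsor within 3 calendar days of site awareness (8.4.2). Appendix A has the CEC classify hospitalizations as heart failure or other cardiovascular.

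**The concern.** At-risk time for the all-cause endpoint runs to the data cut-off, but in the stretch since the last visit only HF admissions are actively sought. Two things follow.

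- Non-HF admissions in that stretch enter the database only if the site learns of them in the ordinary way.
- The sweep question rests on someone calling the admission heart failure. Subjects and some site staff know the assignment (Protocol 10.14), whereas the plan tries to keep the CEC blinded (10.4). The endpoint is also broader than the everyday term. Appendix A counts other admissions that are complicated and prolonged by worsening heart failure needing intravenous or invasive treatment. SAP Section 4.2 adds admissions for mitral valve surgery, LVAD or transplant, and some MitraClip admissions in the Control group. A question about heart failure hospitalizations may not bring these up.

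The all-cause endpoint has about 80% stated power. Because the sequence is fixed, failure there would end formal testing of NYHA class, LVEDV, mortality superiority and the 30-day composite.

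**Working it through.** **1. The plan's own figure.** SAP Section 5.8.4.8 assumes 1.9 (Control) and 1.4 (Device) all-cause hospitalizations per 12 months. RRR = 1 − 1.4/1.9 = 26.3%, against a stated 26%. (The text there calls this an HF reduction, but the rates are all-cause.) Power was checked with 600 simulated trials of 305 per arm, using SAP Section 5.8.2 inputs:
- Gamma frailty with mean 1 and variance 1, shared by hospitalization and death
- 12-month mortality of 27% and 22%
- withdrawal of 7.5% per year

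A negative binomial rate model with dispersion 1 stood in for the joint frailty model. Two-sided 5% power was 79.5% or 78.0%, depending on whether mortality is calibrated marginally or conditionally on frailty. The stated figure of about 80% is reproduced to within about 2 points.

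**2. Share of the endpoint that is not queried.** SAP Section 5.8.2 gives HF rates of 0.6 and 0.42.
- Control non-HF: 1.9 − 0.6 = 1.3, or 1.3/1.9 = 68% of admissions
- Device non-HF: 1.4 − 0.42 = 0.98, or 0.98/1.4 = 70%
- Implied non-HF RRR: 1 − 0.98/1.3 = 24.6%, against 30% for HF

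**3. Length of the stretch.** From the windows in Protocol Table 1, a 12-month visit on day 351 and an 18-month visit due by day 578 leave 578 − 351 = 227 days. An 18-month visit on day 518 and the 24-month point on day 731 leave 213 days. Either is about seven months.

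**4. Person-time affected.** The documents do not give accrual before February 2016. The assumption is that 220 subjects (11 months at the SAP's 20 per month) are 13 to 24 months from randomization at the sweep and the rest have 24 months. The range tried is 120 to 330 subjects.
- Hand check: for 13 to 18 months the mean time since the 12-month visit is 3.5 months. For 18 to 24 months the mean time since the 18-month visit is 3 months. The average is (5 × 3.5 + 6 × 3)/11 = 3.23 months. 220 × 3.23/12 = 59.2 person-years before death and withdrawal.
- At 1.5 years, survival under the marginal calibration is 1/(1 + 1.5 × 0.370) = 0.643 (Control) and 1/(1 + 1.5 × 0.282) = 0.703 (Device), mean 0.673. The hazards are 1/0.73 − 1 and 1/0.78 − 1. Retention is 0.925^1.5 = 0.890. 59.2 × 0.673 × 0.890 = 35.4 person-years.
- Simulation: 36.5 of 818.9 person-years (4.5%) marginally, and 38.1 of 842.7 (4.5%) conditionally. The range is 2.4% (120 late subjects) to 7.0% (330).

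**5. Worst case: no non-HF admission after the last visit is recorded.**

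| | Marginal | Conditional |
|---|---|---|
| Non-HF admissions lost | 28.5 | 31.4 |
| All admissions | 1,078 | 1,136 |
| Lost, % of all | 2.6% | 2.8% |
| RRR, full capture | 25.6% | 25.4% |
| RRR, with gap | 25.9% | 25.7% |
| Power, full capture | 79.5% | 78.0% |
| Power, with gap | 79.3% | 78.8% |

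A robust Poisson fit, which has lower power throughout, goes from 73.3% to 72.2% and from 71.0% to 70.5%. With 600 trials, each power has a standard error of about √(0.795 × 0.205/600) = 1.6 points.

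**6. If the device has no effect on non-HF admissions** (1.3 in both arms), losing them gives HF admissions more weight. Across the accrual range the crude RRR rises by about 0.1 to 0.6 points, for example from 4.5% to 5.0% with 220 late subjects.

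The visits are placed at exactly 12 and 18 months, and subjects exempt because of a visit within 30 days are not removed, which slightly overstates the gap.

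**The case against.** The strongest reply is that the sweep supplements the collection of hospitalizations and is not the main route. Every unplanned in-patient admission is an SAE, collected throughout the trial and due within 3 days of site awareness. The SAE exclusion for planned admissions closely matches the exclusion in the all-cause definition, so SAE reporting covers essentially the same events. The sweep also contacts sites, and any admission revealed in that contact is reportable whatever was asked. The test is of a ratio, both arms have the same visit schedule, and similar loss in both arms largely cancels.

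Most of this stands, and it rules out three stronger readings.

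- A reader might infer that non-HF admissions since the last visit are missed, and that the time is counted as hospitalization-free. The documents give a passive route, so the supportable statement is possible under-ascertainment. The SAP also does not say that each subject's data cut-off date is the sweep date.
- A reader might infer that admissions not labelled heart failure never reach adjudication for the primary endpoint. Appendix A already sends hospitalizations to the CEC for classification, and SAP Section 5.1 sends primary and secondary endpoint events there. The label affects only what the sweep itself brings in.
- A reader might multiply 36.5 person-years by the mean non-HF rate of (1.3 + 0.98)/2 = 1.14 and get about 42 lost admissions with a material loss of power. Survivors have lower frailty under the SAP's model, so the figure is about 30, and power hardly moves.

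The reply does not remove the mismatch. HF admissions are SAEs too, yet the plan does not rely on SAE reporting for them at cut-off. The reason for an active query, that sites may not yet know of recent admissions, applies equally to other causes.

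**Conclusion.** The inconsistency is real and of low severity. A confirmatory endpoint uses follow-up to the same cut-off as the primary, but about two-thirds of its expected events are not actively sought in the final between-visit stretch.

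Even on total loss, the RRR moves by about 0.3 points, and power by under 1 point in the model that reproduces the SAP's figure (1.2 points at most in the robust Poisson fit). With SAE reporting working, the loss would be smaller. The direction slightly favours the device, more so if its benefit is confined to HF admissions.

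These figures rest on the SAP's rates, mortality, attrition and frailty, on an assumed accrual pattern, and on a negative binomial stand-in for the joint frailty model. The labelling issue for primary-endpoint capture is not quantified, because the documents give no figure for it. The case for a change rests on its low cost and on matching ascertainment to at-risk time. It does not rest on a large numerical effect.

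**What to change.** In Protocol Section 6.11 and the note under Table 2, have the sweep ask for survival status and the dates of all hospitalizations since the last study contact. Leave cause to the CEC, as Appendix A already provides. No change to the analysis model is needed.

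If the sweep cannot be changed, the alternative is to censor the all-cause endpoint at the last contact at which all admissions were asked about.

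The cost is one broader question in a call already being made, plus some extra records to collect and adjudicate.

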10.14.2 Maintaining Similar Levels of Follow-up

In order to maintain similar levels of contact between the investigational site and subjects, all subjects will have a "Treatment" visit. During the "Treatment" visit for the Control group, subjects will be seen by a HF specialist, and will undergo a physical exam, including vital signs, cardiac health status and evaluation of heart failure medications. Subjects in the Device group will undergo the MitraClip procedure during the "Treatment" visit. The follow-up schedule post-"Treatment" visit is identical for both groups and both groups will be followed by the HF specialist.

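### Section 6.11.1 scripts the 1-week adverse-event question only for subjects who had the procedure, while Table 2 marks it for all subjects: a minor contradiction to reconcile

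*Protocol*

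**What the plan says.** Protocol section 6.11.1 opens with a rule for both arms: "All subjects will be contacted by telephone at the 1-week visit", and "Sites will follow a standardized script for all subjects to minimize bias". It then makes an addition limited to some subjects: "for Device group or roll-in subjects who underwent the MitraClip procedure, the script will include a query about adverse events, including suspected skin injury". It mentions no adverse-event question for Controls.

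Table 2 gives a different picture. Section 6.11 introduces it with the statement that "Table 2 provides a complete listing of required tests and procedures for all subjects through the trial follow-up period". Two neighbouring column headings read "Discharge (Device Group or Roll-in) | 1-Week Phone Contact": the discharge column names the arm and the 1-week column does not. The adverse-event row, "Adverse Events | | X ^c | X | X | X | X | X | X", is blank at screening and marked in all seven later columns, including the 1-week call. A separate row, "Inquiry of Subject Status | | | | | | X", is marked at the 1-week call only.

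Sections 8.4.1 and 8.4.2 require adverse events to be collected for all registered subjects, from randomization for those randomized. Section 10.14.2, on bias control, says the follow-up schedule "is identical for both groups and both groups will be followed by the HF specialist".

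**The concern.** Treatment is not blinded to the subject or to some of the site staff, so equal enquiry in the two arms is one of the few protections for outcomes that begin with a site report. A question put to one arm at 1 week and to the other only at the 30-day visit gives the second arm a longer recall period and more chance for an event to go unmentioned.

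The comparisons at stake are between-arm ones that depend on site reporting. SAP Appendix A.1 compares renal and major vascular complications reported by sites through 12 months after randomization. Recurrent all-cause hospitalization (SAP section 5.6.2.7) is formally tested in the secondary sequence of SAP section 5.9. An event that was never asked about and never recorded cannot be recovered in the analysis.

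**Working it through.** **1. Do the two places conflict?**

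| Point | Section 6.11.1 | Table 2 |
|---|---|---|
| Who is called at 1 week | All subjects | All subjects |
| Who is asked about adverse events | Stated only for Device or roll-in subjects who had the procedure | All subjects |
| Is it only a skin question? | No; skin injury is given as one example | No; it is the general adverse-event row |

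The narrower text cannot be read as the skin question alone, because it covers adverse events generally and Appendix C separately asks for the skin question at the same call. The subject-status row in Table 2 does not stand in for the adverse-event question, because the table lists both. A site writing its script from section 6.11.1 and a site working from Table 2 could therefore treat Controls differently.

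**2. Timing if section 6.11.1 is followed literally.** Table 1, counted from the Treatment visit, gives the 1-week call as days 6 to 10 (target 7) and the 30-day visit as days 27 to 44 (target 30). The delay to the first scripted question in Controls is:
- on target days: 30 - 7 = 23 days;
- shortest: 27 - 10 = 17 days;
- longest: 44 - 6 = 38 days.

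If Table 2 is followed, both arms are asked at days 6-10 and the delay is zero.

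**3. Which analyses are exposed.**
- Primary safety endpoint and 30-day composite: not exposed. Both are one-group tests in Device subjects with a procedure attempted (SAP sections 5.4.4, 5.5.1, 5.5.2.1).
- Renal and vascular complications for CMS: exposed, being site-reported and compared between arms, though outside the testing sequence.
- Stroke and TIA for CMS: less exposed. They are adjudicated, and the modified Rankin Scale is done at 30 days in both arms, but adjudication still needs an event to be reported or identified first (Protocol section 10.4).
- All-cause hospitalization: possibly exposed.
- Heart failure hospitalization: little exposed, given the later routes of capture described under the objection.

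**4. An order of magnitude for hospitalization.** The SAP gives Control rates but nothing on how many events would be lost. Take a constant rate, a loss of 10-20% of events up to day 10 in Controls, and no loss in Device. These are assumptions with no source in the documents.
- All-cause: 1.9 × 10/365 = 0.052 per subject, or 0.052 × 305 = 15.9 Control events by day 10. Loss: 1.6 to 3.2 events.
- Heart failure: 0.6 × 10/365 = 0.0164 per subject, or 0.0164 × 305 = 5.0 events. Loss: 0.5 to 1.0 event.
- As a share of 12 months of Control events, either way: (10/365) × 10-20% = 0.27% to 0.55%.
- Planned heart failure ratio: 0.42/0.60 = 0.700, a 30% reduction. At the larger loss: 0.42/(0.60 × 0.9945) = 0.704, a 29.6% reduction.
- Planned all-cause ratio: 1.4/1.9 = 0.737, a 26.3% reduction. At the larger loss: 1.4/(1.9 × 0.9945) = 0.741, a 25.9% reduction.

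The documents give no early Control rates for the renal or vascular composites, so no such figure can be worked out for them.

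**The case against.** The strongest reply is that nothing bars sites from asking Controls. The script is not in the documents, Table 2 is declared complete for all subjects, and its 1-week column requires the question. This stands. A reader might infer that Controls are called and not asked, but that is only the literal reading of one of two conflicting places.

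A reader might also take section 10.14.2 to be contradicted. It is not: it speaks of the visit schedule, which is the same in both arms, and not of what is said on the call.

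Other routes of capture also count. Adverse events are collected whether reported by the subject, observed, or found in medical records (section 8.4.1). A form is required for heart-related visits at any facility (section 6.12). Table 2 marks adverse events at the Control Treatment visit, although section 6.10 does not list them there. Both arms are assessed at 30 days. For heart failure, an event generally needs at least 24 hours in hospital with intravenous or invasive treatment, Controls see the heart failure specialist at 30 days, and a later sweep asks about heart failure hospitalizations. Such an admission is unlikely to stay hidden. The sweep is narrow, though: it covers death and heart failure hospitalization only, and it omits subjects with a recent visit or a completed 24-month visit.

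Finally, missed Control events would mostly make the device look worse, so they would not manufacture a benefit. That limits the harm but leaves the contradiction in place, because a safety comparison tilted against the device is still inaccurate.

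**Conclusion.** Wrong as written, as an internal contradiction, and minor. Section 6.11.1 and Table 2 disagree on whether the 1-week adverse-event question goes to all subjects, and the narrower version fits poorly with the bias-control purpose that section 6.11.1 itself gives for the common script.

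If the narrower version is applied, the plausible effect is modest under-recording of early Control events in site-reported comparisons, chiefly renal and vascular complications for CMS and possibly all-cause hospitalization, mostly to the device's disadvantage. The amount cannot be derived from the documents; the hospitalization figures above depend on assumed loss rates and show only that a shift of a few tenths of a point in the relative reduction is the scale to expect under them.

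A reader might infer that the primary effectiveness result is biased. The documents do not support that, given the event definition and the repeated later capture in both arms.

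**What to change.** In section 6.11.1, put one identical question on adverse events and hospitalizations in the 1-week script for all subjects, as Table 2 already indicates for adverse events. Keep only the skin-injury question specific to subjects who had the procedure, consistent with Appendix C. The cost is a sentence in the protocol and a matching edit to the site script; no call or visit is added.
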